17. APPENDICES76

1. OBJECTIVES

1.1 Study Design

This study was designed to enroll 50 subjects with untreated chronic lymphocytic leukemia/small lymphocytic lymphoma (CLL/SLL) who meet IWCLL 2008 criteria for initiation of therapy will initiate single-agent idelalisib (GS1101), a PI3K delta specific inhibitor, daily for the first two months on study, and begin ofatumumab at the start of the 3rd month following a complete response evaluation. The duration of combination therapy will be 8 months. All subjects will receive 8 weekly doses of ofatumumab, following which they will undergo another response evaluation. They will then continue with idelalisib during their 4 monthly doses of ofatumumab. The final primary endpoint response evaluation will occur two months after completion of ofatumumab, at 10 months following start of therapy. Therapy with idelalisib will continue throughout the ofatumumab therapy and after, until development of progressive disease. Once participants are receiving single agent idelalisib therapy they will be seen in clinic every 2 months. After treatment is complete subjects will be followed every 3-6 months at the treating investigator's discretion until initiation of a new therapy or death. Subjects who do not complete cycle 2 are not considered evaluable for the study efficacy objectives and may be replaced. Their data will be included in all toxicity evaluations.

As of 3/11/2016, Gilead has observed an excess of infectious deaths in three trials, one in upfront CLL, and as a result the FDA and Gilead are discontinuing enrollment to upfront CLL trials as well as discontinuing the administration of idelalisib to patients previously enrolled on these trials. All patients on this trial however may receive ofatumumab as planned and continue to be followed per protocol. Correlative analyses will continue as previously planned.

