1.2 Primary Objectives

To determine the ORR of ofatumumab and idelalisib in previously untreated CLL/SLL participants in need of therapy

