9. STUDY CALENDAR

Screening evaluations are to be conducted within 14 days prior to start of protocol therapy. Scans and Bone Marrow Biopsies must be done ≤ 4 weeks prior to the start of therapy. In the event that the participant's condition is deteriorating, laboratory evaluations should be repeated within 48 hours prior to initiation of the next cycle of therapy.

All assessments must be performed prior to administration of any study medication. All study assessments and medications should be administered within ± 3 days of the protocol-specified date during the induction phase and ± 7 days of the protocol-specified date in the post-induction phase, unless otherwise noted.

Table 10

Procedures	Screen	Treatment Phase					Post Induction Phase		Long Term Follow-up	Survival Follow-up
		Cycle 1-2 Idelalisib only (Days 1-56)	Cycle 3 & 4 Weekly Ofa + Idelalisib ¹⁵	Cycle 5-8 Monthly Ofa + Idelalisib	Restage Cycle 4 day 22	Cycle 2 day 22 (Restage end of cycle 2), Cycle 10 day 1 (Final Restage 2 months after end of ofa therapy) and off treatment prior to cycle 10	Cycle 9 Day 1	Every 2 mos while on study drug beginning Cycle 10		
								Every 3 or 6 months ¹¹	Yearly	

CONFIDENTIAL

This document is confidential. Do not disclose or use except as authorized.

Informed Consent	X									
Demography	X									
Medical History	X									
Bone marrow biopsy	X ¹					X ¹		X ¹		
Flow Cytometry by Marrow or blood ¹⁶	X				X	X				
MRD on bone marrow						X				
CT (Chest Abdomen Pelvis)	X ²				X ²	X ²		X ²	X ²	
Tumor Assessment by PE	X				X	X	X	X	X	
CLL FISH panel (on bone marrow)	X					X (ON BONE MARROW)				
Banking at CRC, with Flow Cytometry ³	X	C1 DAY 8 & 15, C2 DAY 1	C3 D8 & 15, C4 D22			X				
DFCI Studies: Genomic Profiling ⁴	X							End of therapy ⁴		
Banking at Clinical Research Consortium for Sites participating in a CRC study ¹⁷	X									
Procedures	Screen	Treatment Phase					Post Induction Phase		Long Term Follow-up	Survival Follow-up
		Cycle 1-2 Idelalisib only (Days 1-56)	Cycle 3 & 4 Weekly Ofa + Idelalisib ¹⁵	Cycle 5-8 Monthly Ofa + Idelalisib	Restage Cycle 4 day 22	Cycle 2 day 22 (Restage end of cycle 2), Cycle 10 day 1 (Final Restage 2 months after end of ofa therapy) and off treatment prior to cycle 10	Cycle 9 Day 1	Every 2 mos while on study drug beginning Cycle 10	Every 3 or 6 months ¹¹	Yearly

CONFIDENTIAL

This document is confidential. Do not disclose or use except as authorized.

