 5. For ofatumumab, 2 lavender top tubes. Predose and end of infusion on cycle 3 day 1, cycle 3 day 8, cycle 3 day 15 and cycle 4 day 22 (end of weekly ofa), and cycles 5 and 8 day 1. Note: Predose only for cycle 3 days 8 and 15; and 2 and 6 mos post therapy, no end of infusion.
- For idelalisib, one lavender top predose and one lavender top 1.5 hours post-dose, on Cycles 1-3 Day 1, Cycle 4 Day 22, Cycle 8 Day 1 (last monthly dose of Ofatumumab) and 2 and 6 months after end of ofatumumab.
6. OSU: 3 ACD (yellow top) tubes, 8.5 cc each, + one sodium heparin (green top) tube at screen; 5 ACDs and one heparin on day 1 prior to therapy, 2 ACDs on cycle 1 day 15, 5 ACDs and one heparin on cycle 2 day 1, 3 ACDs and 1 sodium heparin (green top) tube at two month restage, and 2 ACDs on cycle 3 day 1.
 7. Mayo Clinic: 1 sodium heparinized (10 cc green top) tube. Bone marrow aspirate (a couple ccs) will be obtained at each timepoint. At screening only aspirate should be collected.
 8. SAEs and deaths for six months after completion of all therapy.
 9. Only in women of childbearing potential
 10. For those patients who are hepatitis B core antibody positive but surface antigen and HBV DNA negative, monitoring of HBV DNA or viral load is required during the on treatment period at least every 2 months and during follow-up at a minimum of every 2-3 months up to 12 months after the last dose. This testing is also required in the event of development of grade 1 or more elevation in LFTs.
 11. Subjects who discontinue therapy due to an adverse event, but have demonstrated a response of SD or better will enter the follow-up period and be followed every 3 or 6 months until documented relapse or PD, initiation of a new therapy, or for a total of 12 months of follow-up, whichever occurs first.
 12. Vitals Signs include: heart rate, respiratory rate, temperature, blood pressure and oxygen saturation.
 13. Chemistry: Electrolytes, BUN, creatinine, glucose, LDH, phosphate, uric acid, LFTs (total bilirubin, AST, ALT, alkaline phosphatase). Beginning C1D15 through C4D28 a comprehensive metabolic panel (electrolytes, BUN, creatinine, glucose, LDH, phosphate, uric acid, LFTs (total bilirubin, AST, ALT, alkaline phosphatase) will be obtained twice per week. If grade 1 or higher AST, ALT, or bilirubin elevations are noted please see Section 6.2 "Management of Hepatic AEs."
 14. Hematology: CBC, manual differential
 15. Weekly Ofatumumab proceeds through Cycle 4 Day 22.

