 16. Flow Cytometry should assess at minimum the following markers: CD5+CD19+, CD19+, CD 20+, CD19+CD23+, CD19+CD38+, kappa and lambda surface immunoglobulins.

Footnotes 16 & 17 outline the sample collection for sites that are or are not participating in the CLL Research Consortium tissue bank study, (for more information-Section 8.2.1):

17. Sites participating in a CLL Research Consortium tissue bank study (Section 8.2.1) provide 3 sodium heparinized (green top) tubes of peripheral blood at screening.
18. Sites *not* participating in a CLL Research Consortium (CRC) tissue bank study (Section 8.2.1) provide 3 sodium heparinized (green top) tubes of peripheral blood at screening, cycle 3 day 1 and coming off study due to disease progression or toxicity. In addition, collect a saliva sample at screening.

Off-Treatment Evaluations

If at all possible, patients going off study should have: hematology, chemistry, beta-2-microglobulin, CD4 count, IgG, IgM, IgA, serum protein electrophoresis, full tumor assessment by CT, bone marrow biopsy and samples for correlative studies. Please obtain the following samples described under genomic and Mayo Microvesicle for correlative studies. If prior to cycle 2 day 22 please obtain any additional studies required for that visit.

CONFIDENTIAL

This document is confidential. Do not disclose or use except as authorized.

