10.1.6 Treatment failure

Responses that should be considered clinically beneficial include CR, PR and nodal PR with lymphocytosis; all others (eg, stable disease, nonresponse, progressive disease, or death from any cause) should be rated as a treatment failure.

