14. STATISTICAL CONSIDERATIONS

14.1 Sample Size/Accrual Rate

Primary Objective:

The primary objective for this phase II study is to estimate the overall response rate or ORR (CR+PR) of ofatumumab and idelalisib in previously untreated CLL/SLL.

Hypothesis:

Null: 0.55 ORR

Alternative: 0.75 ORR

Sample size and power calculation:

A two stage design is used to compute the sample size. A total number of 50 eligible patients is needed in order to detect a 75% response rate, assuming the ORR for the null hypothesis is 55%, with 90% power and 4% type I error. 31 patients will be enrolled initially into the study. The study will stop early if only 17 or fewer responses out of 31 patients are observed and the drug will not be declared promising if less than 34 responses are seen in the total 50 patients. The probability of stopping at the first stage is 0.56 if the null hypothesis is true. For the purposes of the two-stage design and in order to avoid potential closure to enrollment, we will use the four month response evaluation to decide about moving to the second stage.

Primary Analysis:

The overall response rate and a 90% confidence interval will also be calculated, using the

CONFIDENTIAL

This document is confidential. Do not disclose or use except as authorized.

method of Atkinson and Brown for a two stage study. Patients' baseline characteristics will be summarized using descriptive statistics (median, interquartile range, proportions).

Enrollment was discontinued at 27 patients and ORR will be estimated based on the data, with 90% confidence interval.

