14.3 Reporting and Exclusions

14.3.1 Evaluation of toxicity. All participants who receive one dose of study therapy will be evaluable for toxicity from the time of their first treatment.

CONFIDENTIAL

This document is confidential. Do not disclose or use except as authorized.

14.3.2 Evaluation of response. All participants included in the study and who actually receive at least one dose of study therapy will be assessed for response to treatment, even if there are major protocol treatment deviations or if they are ineligible. Each participant should be assigned one of the following categories: 1) complete response, 2) partial response, 3) stable disease, 4) nodal response with lymphocytosis; 5) progressive disease, 6) early death from malignant disease, 7) early death from toxicity, 8) early death because of other cause, or 9) unknown (not assessable, insufficient data). By arbitrary convention, category 9 usually designates the "unknown" status of any type of data in a clinical database.

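### The primary ORR denominator is contradictory: 1.1 excludes patients who do not complete cycle 2, 14.3.2 assesses everyone treated, and 14.1 adopts neither

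*Combined protocol and SAP*

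**What the plan says.** Three places bear on which patients enter the primary ORR.

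- Section 1.1 sets an efficacy-evaluability rule: "Subjects who do not complete cycle 2 are not considered evaluable for the study efficacy objectives and may be replaced". The same section keeps these patients in all toxicity evaluations.
- Section 14.3.2, under the heading on reporting and exclusions, says: "All participants included in the study and who actually receive at least one dose of study therapy will be assessed for response to treatment". This applies even to ineligible patients and those with major treatment deviations. Each patient receives one of nine categories, which include progression, three kinds of early death, and unknown.
- Section 14.1 defines ORR as CR plus PR, sizes the trial in eligible patients, and closes with: "Enrollment was discontinued at 27 patients and ORR will be estimated based on the data, with 90% confidence interval". It does not name the analysis set.

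Section 10.1.6 lists the outcomes that it counts as beneficial (complete or partial remission, and a nodal response with lymphocytosis) and then says: "all others (eg, stable disease, nonresponse, progressive disease, or death from any cause) should be rated as a treatment failure".

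**The concern.** The two rules give different denominators for the same primary estimate, and no section reconciles them. The 1.1 rule selects on something that happens after treatment starts. A patient who dies or progresses during the first two cycles is a failure under 10.1.6, yet would leave the efficacy denominator under 1.1. When the rule was written, such a patient could be replaced. With enrolment closed, replacement no longer operates, so the rule can only shrink the denominator.

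This is a single-arm trial with at most 27 patients, and the ORR with its 90% interval is the main efficacy result. If the set is not fixed, it can be chosen after the responses are known. The set is also not well defined, because the protocol does not say whether a patient with held doses, or one stopped on 3/11/16, has completed cycle 2.

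**Working it through.** **1. The plan's own design figures.** Inputs from 14.1: null 0.55, alternative 0.75, first stage 31 with stopping at 17 or fewer responses, total 50, success at 34 or more.

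P(success | p) = sum over x = 18 to 31 of Bin(x; 31, p) × P(Bin(19, p) ≥ 34 − x).

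- At p = 0.55: 0.0424 (stated 4%).
- At p = 0.75: 0.9008 (stated 90%).
- P(Bin(31, 0.55) ≤ 17) = 0.5620 (stated 0.56).

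The design figures reproduce, so the sample size is not in question. The issue is only which patients are counted.

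**2. Who could fail to complete cycle 2.** The study calendar puts cycles 1–2 at days 1–56, and section 5 starts ofatumumab on day 57. Three groups need separate treatment.

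- *Death or progression in cycles 1–2.* PR must be documented for at least 2 months (10.1.2) and CR must still be present at least 2 months after it is first documented (10.1.1). These patients are non-responders, so dropping them shrinks the denominator only.
- *Leaving for toxicity.* The calendar's restaging column covers patients "off treatment prior to cycle 10", and its off-treatment text adds: "If prior to cycle 2 day 22 please obtain any additional studies required for that visit". Footnote 11 says: "Subjects who discontinue therapy due to an adverse event, but have demonstrated a response of SD or better will enter the follow-up period". Such a patient could have a documented response.
- *Stopped on 3/11/16 before day 57.* Section 5 lets these patients start ofatumumab, so they could respond later.

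**3. Effect of dropping.** Let x be the responders among 27 treated, k the number dropped, and r the responders among those dropped.

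Shift = (x − r)/(27 − k) − x/27.

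This is positive when 27(x − r) > x(27 − k), that is, when r/k < x/27. Dropping raises ORR only if the dropped patients respond less often than the whole treated group.

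**4. Illustration.** Assumptions, none of them in the documents: all 27 enrolled were treated, x = 18, and k as shown. Intervals are exact (Clopper-Pearson) 90% limits for a single stage, because enrolment ended before the first-stage size of 31.

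No responder among the dropped (r = 0):

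| k | ORR | 90% CI | Shift (points) |
|---|---|---|---|
| 0 | 18/27 = 66.7% | 49.1–81.4 | 0 |
| 1 | 18/26 = 69.2% | 51.3–83.7 | +2.6 |
| 3 | 18/24 = 75.0% | 56.5–88.5 | +8.3 |

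With k = 3 and some responders among the dropped:

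- r = 1: 17/24 = 70.8%, shift +4.2 points
- r = 2: 16/24 = 66.7%, shift 0.0
- r = 3: 15/24 = 62.5%, shift −4.2 points

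**The case against.** **Assessment is not the denominator.** Section 14.3.2 can be read as a rule for classifying every treated patient, with 1.1 deciding who enters the efficacy estimate. It is true that 14.3.2 never says that all nine categories enter the ORR denominator. But no section says that 1.1 governs instead, and on that reading the primary estimate would still omit early failures.

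**The target is the combination.** The primary objective is "To determine the ORR of ofatumumab and idelalisib in previously untreated CLL/SLL participants in need of therapy", and under the original schedule a patient who left before day 57 never received ofatumumab. A set restricted to patients who reached the combination answers a sensible activity question, and ORR on that set is too high only as an estimate for everyone who started treatment. This stands as a reason to report that set. It does not settle the primary set, because no section gives it as the purpose of the rule.

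**There may be nobody to drop.** The documents report no death or progression before day 56. Isolated lymphocytosis does not count as progression (10.1). The early problem they do describe is transaminitis (2.5), and 6.2 allows holds of up to six weeks without removal from study. All of this stands: k may be zero.

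**27 is the number enrolled.** Sections 4.1 and 4.3 let a registration be cancelled when no therapy is given, and 14.1 does not say that 27 patients were dosed. This stands, and the illustration carries it as an assumption.

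**Conclusion.** The concern holds in this form: the primary ORR has two incompatible evaluability rules, and the primary analysis section adopts neither. Under 1.1, any early death or progression leaves the denominator and ORR rises relative to all treated patients. For patients who left for toxicity, or were stopped on 3/11/16, the direction depends on whether they responded. The size is unknown. The shifts of +2.6 points (k = 1) and +8.3 points (k = 3) rest on 27 treated, 18 responders and no responder among the dropped.

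A reader might infer more, and the documents do not support it:

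- *That the plan gives no denominator at all.* It does give a rule, in 1.1. The fault is that 14.3.2 points the other way and 14.1 does not choose.
- *That the ORR will in fact be inflated.* Neither the number of non-completers nor their outcomes are given.
- *That a test against 55% is compromised, or its false-positive rate raised by replacing early failures.* After closure 14.1 plans only an estimate with an interval, and replacement has ended. An interval limit falling on one side or the other of 55% is not a decision criterion.

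This should be fixed because it concerns the primary estimate, but the harm is confined to that estimate and its interval, and to the CR rate if the same set is used.

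**What to change.** In 14.1, state that the primary ORR is CR plus PR divided by all patients who received at least one dose, consistent with 14.3.2. Credit any documented CR or PR regardless of early stopping, and count everyone else as a non-responder, including early deaths and category 9 (unknown).

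In 1.1, amend the evaluability sentence so that cycle-2 completers form a labelled sensitivity analysis for patients who reached the combination. For that analysis, define completion of cycle 2 when doses were held and when treatment stopped on 3/11/16. Report how many patients did not complete cycle 2 and why, together with the number treated.

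The cost is wording in two sections, with no new data. The reported ORR may be slightly lower, and it would include some patients who never received ofatumumab; the sensitivity analysis shows how much that matters.

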1.2 Primary Objectives

To determine the ORR of ofatumumab and idelalisib in previously untreated CLL/SLL participants in need of therapy

1.3 Secondary Objectives

To determine the CR rate and PFS of ofatumumab and idelalisib.

To determine the ORR, CR rate and rate of nodal PR with lymphocytosis for idelalisib given alone for two months of therapy to previously untreated participants

To determine the rate of lymphocytosis with idelalisib in previously untreated participants

To assess the safety of idelalisib in untreated participants and in combination with ofatumumab.

To determine whether clinical response correlates with known CLL molecular prognostic factors including FISH, *IGHV*, *ZAP-70*.

CONFIDENTIAL

This document is confidential. Do not disclose or use except as authorized.

To determine whether the use of CT scans in response assessment improves the predictive power of ORR for progression-free survival or time to next treatment.

To determine whether serum ofatumumab and/or idelalisib levels in vivo predict response.

To assess whether initial treatment with idelalisib alters the cell surface marker phenotype of circulating CLL cells.

To assess whether in vivo treatment with idelalisib alters CLL cell sensitivity to therapy with antibodies or other kinase inhibitors.

To assess pharmacodynamic markers of PI3 kinase inhibition including AKT phosphorylation, production of T cell chemokines and response to CXCR 4/5.

To determine whether response or resistance correlates with genetic alterations in PIK3CA or PIK3CD or other genes.

To determine the influence of idelalisib treatment on intrinsic innate immune suppression and on regulatory T cells.

To identify predictors of response and resistance to idelalisib through biochemical and genetic analysis of the PI3K pathway.

To assess the clonal dynamics of CLL in peripheral blood vs bone marrow, and during therapy with idelalisib.

2. BACKGROUND

2.1 Preclinical Characterization of Idelalisib

Nonclinical efficacy pharmacology data in enzyme-based and cell-based systems indicate that idelalisib is a potent inhibitor of PI3K δ but that its selectivity spares other PI3K isoforms and other kinases. Testing in nonclinical models of lymphoid neoplasia confirm the importance of the PI3K δ pathway in these tumor types, and document idelalisib activity in suppressing the growth and survival of these malignancies [1, 2].

In in vitro assays evaluating PI3K enzymatic activity, idelalisib potently inhibited PI3K δ , with a concentration inducing 50% inhibition (IC₅₀) of 2.5 nM. By contrast, IC₅₀ values for the effects of idelalisib on PI3K α , PI3K β , and PI3K γ were 820, 565, and 89 nM respectively, indicating a selectivity of idelalisib for PI3K δ that is 40- to 300-fold greater than for other PI3K Class I family members. When assessing IC₅₀ values relative to Class II, III, and IV PI3K enzymes, idelalisib showed 400- to 4000-fold greater activity for Class I PI3K δ inhibition. In vitro selectivity was further demonstrated by evaluation of activity against the comprehensive panel of

CONFIDENTIAL

This document is confidential. Do not disclose or use except as authorized.

402 kinases in the Ambit KinomeScan; idelalisib at 10 μM (0.42 $\mu\text{g}/\text{mL}$) inhibited PI3K enzymes but showed no activity against other enzymes.

Potency and selectivity have been confirmed in cell-based *in vitro* assays. In human whole blood, idelalisib potently inhibited basophil activation via a PI3K δ -dependent pathway, with an EC_{50} of 62 nM; by contrast, inhibition of basophil activation via a PI3K γ -dependent pathway showed an EC_{50} of 4,456 nM. Idelalisib also showed potent *in vitro* inhibition of PI3K δ -mediated processes in other cell types; activation of human B-cell proliferation via the B-cell receptor, neutrophil degranulation in response to bacterial peptide, and stimulation of human T-cell proliferation via the T-cell receptor were inhibited with respective EC_{50} values of 8 nM, 119 nM, and 932 nM. By contrast, when examining PI3K α - or PI3K β - mediated phosphorylation of AKT in primary mouse fibroblasts, idelalisib showed EC_{50} values of $>20 \mu\text{M}$ and 1900 nM, thus substantiating the lack of idelalisib effect on signaling via these PI3K isoforms.

Consistent with the moderate to high bioavailability seen in nonclinical species, idelalisib shows high permeability across human Caco-2 cell monolayers. At lower concentrations, the reverse permeability at low concentration exceeds forward permeability, indicating efflux driven by transporters (for e.g., human P-glycoprotein (MDR1) and breast cancer resistance protein (BCRP)); idelalisib is a substrate for the efflux transporters MDR1 and BCRP; however, the permeability increases in a concentration-dependent manner, resulting in a lower efflux ratio at higher, clinically relevant concentrations of idelalisib.

Idelalisib exhibits moderately high plasma protein binding in mouse, rat, dog, and human. In dog and human plasma, the protein binding is concentration-independent between 1 and 20 μM . Protein binding in human plasma is slightly higher than in mouse, rat, and dog plasma, which have comparable free fractions. In human plasma, idelalisib and GS-563117 (a metabolite of idelalisib) have an average free fraction of $\sim 16\%$ and $\sim 12\%$, respectively.

After oral administration of [^{14}C]idelalisib to rats and dogs, radioactivity is widely distributed, but relatively excluded from bone, brain, spinal cord, and eye lens in rats and from brain and eyes in dogs. In rats, the radioactivity declines steadily and most tissues have undetectable levels by 72 hours post dose. In bile duct-cannulated rats and dogs, $\geq 69\%$ of radioactivity is recovered in bile and urine, indicating high absorption of idelalisib *in vivo*.

In hepatic tissues from nonclinical species, idelalisib is primarily metabolized by aldehyde oxidase, CYP3A, and UGT1A4. *In vitro* metabolism in dog and human yields 3 primary oxidative metabolites and 5 primary glucuronides. Of these, the oxidative product GS-563117 is the predominant metabolite *in vitro* and *in vivo*. In preclinical species, plasma levels of GS-563117 are below those of idelalisib. However, in humans GS-563117 plasma levels significantly exceed those of idelalisib. After oral administration of [^{14}C]idelalisib to rats and dogs, biliary excretion appears to be the major route of elimination of idelalisib and its metabolites as the majority of radioactivity is found in feces or bile and little in urine.

CONFIDENTIAL

This document is confidential. Do not disclose or use except as authorized.

Idelalisib is not a substrate for the renal transporters OCT2, OAT1, and OAT3 or the hepatic uptake transporters OATP1B1 and OATP1B3. GS-563117 is not a substrate for OATP1B1 and OATP1B3.

Idelalisib shows insignificant inhibition of CYP1A, CYP2B6, CYP2C9, and CYP2D6, and modest/moderate inhibition of CYP2C8 ($IC_{50} = 13 \mu\text{M}$), CYP2C19 ($IC_{50} = 76 \mu\text{M}$), and CYP3A ($IC_{50} = 44 \mu\text{M}$). GS-563117 shows insignificant inhibition of CYP1A, CYP2B6, CYP2C8, CYP2C9, CYP2C19, and CYP2D6, and is a moderate inhibitor of CYP3A ($IC_{50} = 3.1 \mu\text{M}$).

Idelalisib shows insignificant inhibition of the transporters BCRP, OCT2, OAT1, and OAT3, and modest/moderate inhibition of MDR1 ($IC_{50} = 7.7 \mu\text{M}$), OATP1B1 ($IC_{50} = 10.1 \mu\text{M}$), OATP1B3 ($IC_{50} = 7.0 \mu\text{M}$), and the glucuronosyltransferase UGT1A1 ($IC_{50} = 42.0 \mu\text{M}$). GS-563117 shows insignificant inhibition of MDR1, BCRP, OATP1B1, OATP1B3, OAT1, OAT3, and OCT2, and moderate inhibition of UGT1A1 ($IC_{50} = 16.8 \mu\text{M}$).

In support of clinical development in patients with lymphoid cancers, idelalisib has undergone toxicological evaluation in conformance with the International Conference on Harmonisation (ICH) S9 guidance on nonclinical evaluation for anticancer pharmaceuticals

